We will use a blocked randomization design based on gender, with a goal of equal representation of males and females. Participants will be randomized to the standard of care (referral to initiate ART) or the intervention arm. A computerized random-number generator will be used to formulate an allocation schedule; participants will be given their assigned allocations within sealed opaque envelopes. The RA enrolling patients will be blinded to the randomization assignment. Upon completion of the baseline questionnaire, the randomization assignment will be revealed. For participants randomized to the TAP arm, the RA will notify the TA, who will come to meet the participant immediately upon completion of the survey. We will seek to prevent control group contamination (i.e., controls being influenced by what the intervention group is learning). For contamination to threaten the ability to detect intervention effects, statistical models suggest that $\geq 30\%$ of the control group must receive the equivalent of a full-strength intervention², which we believe to be highly unlikely. Nevertheless, we will survey participants about possible contamination (e.g., whether they discussed this study with community members) upon study completion.

Data collection.

Primary Outcome. ART initiation – Assessed at the completion of the intervention (month 3) and monthly through 6 months post-intervention. This will be measured through both self-report, medical records at GCHC, and accessing data through the NHLS.

Demographics. We will collect baseline demographic data, and HIV clinical data (diagnosis date, clinical history, most recent CD4 count).

Laboratory testing. Standard protocol at the testing center is testing of the participant's blood to determine HIV status and CD4 and participant eligibility. This is done routinely already at GCHC.

Self-Report Measures. We will administer two sets of surveys to the pilot groups (baseline and at completion of the intervention) to test survey questions and tracking procedures. Our current

study in Gugulethu utilizes an interviewer-administered survey that has been shown to be feasible. Participants will complete the baseline survey before randomization. Code numbers will link data over time. Intervention participants who drop out of the program will be encouraged to complete all surveys.

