Primary data analysis will be an intent-to-treat analysis, which includes all randomized participants. Of note, every attempt will be made to continue assessing participants even if they drop out of treatment. In addition, we will replicate all analyses with the completers only. The hypothesis that The Treatment Ambassador Program will yield higher rates of ART initiation by the completion of the intervention will be tested using Fisher's exact test; the treatment effect estimate will be summarized in terms of a relative risk and 95% confidence interval. Any baseline demographic or clinical variables identified as necessary covariates in preliminary analyses will be included in a logistic regression analysis that examines the main effect of treatment condition on the rates of ART initiation.

Power/Sample Size Considerations. Because this is a pilot study, power considerations for testing null hypotheses are somewhat less relevant than having adequate degrees of freedom to estimate treatment effects with a reasonable degree of precision for potential use in a future fully-powered trial. However, for completeness, we present a summary of the power analyses for the primary hypothesis below. With a sample size of up to 45 per treatment group, the probability is greater than 80 percent that the study will detect a difference of 25% in the percent who initiate ART. This is based on the assumption that the percent who initiate ART in the control group is approximately 10%, as seen in our prior research in SA. Thus, the study is adequately powered to detect medium-to-large effect sizes (corresponding to a relative risk = 3.5) for the primary outcome. Finally, allowing for a dropout or attrition rate anticipated to not be greater than 10%, we plan to recruit a total of up to 90 participants (45 per group) to ultimately guarantee our complete sample of 80 participants. This proposed sample size provides more than sufficient degrees of freedom to obtain a precise estimate of the primary outcome event rate and a preliminary relative risk

comparison of the two treatment groups, even when allowing for up to 10% loss to follow-up. If promising results are detected, these data will provide an estimate of the reliability of the intervention effect to inform power calculations for a larger RCT.

Process Evaluation to Examine the Feasibility and Acceptability of the Intervention.

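### The 30% contamination tolerance is not supported by the plan's own sample size and rates: power falls materially well below that level

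*Combined protocol and SAP*

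**What the plan says.** In the protocol's section on randomization for the RCT, the plan cites statistical models for the statement that detection is threatened only when at least 30% "of the control group must receive the equivalent of a full-strength intervention". It considers that level highly unlikely. As a further safeguard it adds that "we will survey participants about possible contamination (e.g., whether they discussed this study with community members) upon study completion".

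The section on power and sample size gives the design inputs. "With a sample size of up to 45 per treatment group", it says, "the probability is greater than 80 percent" of detecting a 25-point difference, on the assumption that "the percent who initiate ART in the control group is approximately 10" per cent. The effect is described as "corresponding to a relative risk = 3.5". The primary comparison uses Fisher's exact test. Neither alpha nor sidedness is stated, and the power statement makes no allowance for contamination. The same section says that power matters somewhat less because this is a pilot.

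**The concern.** The 30% figure is a claim about the ability to detect an effect, so it can be tested against the design that has to do the detecting. The documents show no such test. A design planned at just over 80% power has little to spare, and any control who gains from the intervention raises the control rate and shrinks the contrast.

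Two things are at stake. The first is interpretation: a reader who accepts the tolerance could set aside contamination below 30% when considering a weak or null result. The second is what the pilot passes on. The plan intends to use the estimated effect to inform power calculations for a larger RCT, and an effect diluted by unmeasured contamination would enter those calculations unrecognised.

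**Working it through.** **Inputs.** From the power section: n = 45 per arm, control rate 0.10, difference 0.25, hence intervention rate 0.35 (0.35/0.10 = 3.5, which agrees with the stated relative risk). The primary test is Fisher's exact test. Two-sided alpha 0.05 is assumed; it is consistent with the planned 95% confidence interval. One-sided results are also shown because the hypothesis is directional.

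**Reproducing the plan's figure.** Pooled normal approximation, no continuity correction, two-sided 0.05:

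- power = Φ[(d − 1.96·SE0)/SE1], where SE0 = √(2·p̄(1−p̄)/n) and SE1 = √([p1(1−p1) + p2(1−p2)]/n)
- p̄ = 0.225; SE0 = √(2×0.225×0.775/45) = 0.0880; SE1 = √((0.0900+0.2275)/45) = 0.0840
- (0.25 − 0.1725)/0.0840 = 0.922, so power = 82.2%

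This matches the stated value above 80%. The planned two-sided Fisher test gives 76.2% for the same inputs (binomial probabilities summed over all 2×2 tables with p ≤ 0.05).

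**Adding contamination.** If a share c of controls receives the full-strength equivalent, the control rate is 0.10 + 0.25c and the intervention rate stays at 0.35.

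| c | Control rate | Difference (points) | Expected RR | Fisher, two-sided | Pooled, two-sided | Fisher, one-sided | Pooled, one-sided |
|---|---|---|---|---|---|---|---|
| 0% | 10.0% | 25.0 | 3.5 | 76% | 82% | 85% | 89% |
| 10% | 12.5% | 22.5 | 2.8 | 63% | 72% | 75% | 81% |
| 20% | 15.0% | 20.0 | 2.3 | 50% | 59% | 63% | 71% |
| 30% | 17.5% | 17.5 | 2.0 | 38% | 47% | 51% | 60% |

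With 40 per arm (the plan's 80 completers), two-sided Fisher power is 72%, 59%, 46% and 34%.

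**Weaker exposure.** If exposed controls gain half the effect, the control rate is 0.10 + 0.125c, so exposure of 10%, 20% and 30% acts like full-strength exposure of 5%, 10% and 15%. Two-sided Fisher power is then 70%, 63% and 57%.

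**Effect on the next trial.** With the pooled two-sided formula at 80% power, the sample size per arm implied by 10% against 35% is 43. It becomes 55 for 12.5% against 35% and 99 for 17.5% against 35%.

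**The case against.** The strongest reply is that the scenario is remote. The intervention is eight 60-minute sessions with peer support and navigation from an assigned, trained Treatment Ambassador. Three ambassadors take 12–14 participants each, 36–42 in all, which does not exceed the intervention arm. Full-strength contamination of 10% would mean 4 or 5 of 45 controls receiving the equivalent of all that. Contamination by conversation would be weaker and cost less power. This stands as an argument about likelihood, and nothing in the documents rebuts it. It does not support the different claim that anything below 30% leaves detection unthreatened.

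The pilot purpose also counts. The phase is aimed mainly at acceptability and feasibility, which lowers the weight of power. It does not lower the weight of the effect estimate, which the plan wants for the larger trial.

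Three stronger readings are tempting and should not be drawn:

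- **That contamination takes power from above 80% to 63% or 38%.** About 6 points of that gap (82% to 76%) come from using Fisher's test instead of the pooled approximation. The right starting point for 63% and 38% is 76%.
- **That receipt of the intervention goes unmeasured.** Discussion with community members is given only as an example, and the full set of items is not shown. Ambassador contacts are to be logged, attendance registers kept, and problems in both conditions documented.
- **That the cited model is wrong or was misapplied.** Its assumptions, and what it meant by a threat to detection, cannot be seen from the documents. No decision rule in the plan ties the survey to 30% either.

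**Conclusion.** The point holds as a correction to a stated robustness property. On the plan's own rates and sample size, 30% is not a safe threshold. Full-strength contamination at that level leaves power between 38% and 60% across the four test choices, and 10% costs 8 to 13 points. On the most favourable choice, the one-sided pooled test, 10% contamination still leaves power just above 80%, so the size of the loss at low contamination depends on choices that the plan has not stated.

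The headline figures rest on two assumptions: two-sided alpha 0.05, and exposed controls reaching the full 35% rate. The second follows the plan's own full-strength wording; under half-strength exposure, 30% contamination lowers two-sided Fisher power from 76% to 57%. The documents do not show that contamination at any of these levels is to be expected, and that is not claimed here.

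**What to change.** 1. Delete the 30% tolerance. In its place give power and expected relative risk at 0, 10, 20 and 30% contamination, naming the test, alpha, sidedness and the full-strength assumption. The view that substantial full-strength contamination is unlikely can stay as a separate statement.
2. Make sure the contamination items planned for study completion ask controls about receipt: contact with a Treatment Ambassador, sessions attended and content received. Report the exposed share of controls by degree of exposure.
3. Do not divide the risk difference by (1 − c) with c counted from any contact. If 30% of controls reported contact that had no effect, a true 25-point difference would become 25/0.7 = 36 points. If an adjusted figure is shown, label it an upper-bound sensitivity estimate and count only controls with full-strength exposure.

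The cost is protocol wording, a few items in a survey already planned, and a less favourable robustness statement. No study procedure for participants changes beyond those items.

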Incentives and Efforts to Improve Response Rates. We have extensive experience retaining participants over time in SA. We will offer participants choices as to where they would like to do the survey, and they will receive a stipend of Rand 100 (roughly \$8 U.S for each of the surveys, with a Rand 200 bonus at the end for completing all 3 surveys).

Quality Assurance. For each session, TAs will fill out a quality assurance form to assess the extent to which key elements and activities from the program manual were covered. We will record each session, and independent raters on the SA team will code the extent to which key elements were covered; $\kappa \geq .70$ will indicate adequate consistency between coders.

Curriculum Revision. The curriculum development team (Drs. [name], [name], [name], and [name]) will thoroughly review and discuss results with the CAB annually. These discussions will help us to optimize our RCT. For this phase, we intend to pilot test the Treatment Ambassador intervention on a sample of up to 45 PLWH in each group (up to $n=90$) who have not started ART within 3-6 months of learning eligible. This phase of the study is focused on assessing acceptability and feasibility to inform a larger RCT. Inclusion criteria, recruitment, intervention, TA training and supervision, outcomes and measures, are described above, pending refinement based on our iterative design. In preliminary analyses, randomized groups will be compared with respect to baseline demographic and clinical variables using t-tests and chi-square tests; if significant group differences are identified in any variables known to be highly predictive of ART initiation outcome, these variables will be adjusted for via their inclusion as covariates in analyses. These covariates will also be summarized with descriptive statistics and graphical methods to determine the most appropriate way to incorporate them in the analyses (e.g., continuous or categorical representation of the variable).

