Process evaluation analysis. We will use an inductive content analytic approach to analyze qualitative data. This approach consists of the following steps: (1) data reduction through coding, (2) category construction, (3) comparison, and (4) interpretation.

Coding. Coding will begin with a provisional start-list of themes based on prior research. Twenty percent of the interviews will be independently read and new themes iteratively generated based on identifying themes not present in the start-list, which will result in a codebook. The team members will code 20% additional interviews to calibrate the methods of evaluation, and one individual, using the standards established, will code the remaining interviews (Cohen's Kappa ≥ 0.80). For each of the seven survey measures, we will compare responses at 6 months by computing the mean response for each arm, a 95% bootstrap confidence interval for the between-arm difference in means, and a permutation test p-value for the between-arm difference in means adjusted for each participant's baseline score. To assess preliminary efficacy, rates of ART initiation at 3 months for the two arms will be

compared by computing the relative “risk” of initiation and testing for an association between arm and initiation rate using Fisher’s exact test.

We will use NVivo10[©] (QSR International Pty Ltd 2014) software to code and manage the data. The result will be a reduced data set consisting of an initial set of concepts and corresponding sections of interview/field note text -- the basis for category construction. Categories will be developed by grouping codes and coded data into meaningful clusters to form larger concepts. We will formulate labels and definitions for each new concept. Final versions of categories will include: (1) the category label or name, which should convey a category’s essential meaning; (2) the operational definition and/or an indication of the variety of specific forms the category takes; and (3) evidence of validity in the form of examples of the data from which the category was formulated. The role of interpretation here is to develop conceptual categories into larger explanations to guide process evaluations.

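### Gender is the blocking factor but is absent from the Fisher/relative-risk analysis, covariates enter only through a baseline significance screen, and the stated power does not fit a two-sided Fisher test: a modest efficiency and pre-specification point

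*Combined protocol and SAP*

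**What the plan says.** The section on RCT randomisation states: "We will use a blocked randomization design based on gender, with a goal of equal representation of males and females". Recruitment Procedures adds 1:1 allocation and a commitment to gender balance.

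The primary analysis paragraph assigns Fisher's exact test to the main hypothesis ("The hypothesis that The Treatment Ambassador Program will yield higher rates of ART initiation by the completion of the intervention will be tested using" that test) and gives the effect as a relative risk and 95% confidence interval. The process evaluation analysis repeats this for month 3: a relative risk, and "testing for an association between arm and initiation rate using" Fisher's exact test. Neither place mentions gender.

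The preliminary analyses, described just before, compare the arms at baseline with t-tests and chi-square tests and then apply the rule: "if significant group differences are identified in any variables known to be highly predictive of ART initiation outcome, these variables will be adjusted for". No predictor is named, no significance level is given for the screen, and covariate form is to be chosen after looking at the data. The adjusted model inherits the result: "Any baseline demographic or clinical variables identified as necessary covariates in preliminary analyses will be included in a logistic regression analysis".

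Under Power/Sample Size Considerations: "With a sample size of up to 45 per treatment group, the probability is greater than 80 percent that the study will detect" a 25-point difference from a control rate of about 10%, that is, a relative risk of 3.5. Up to 90 are recruited "to ultimately guarantee our complete sample of 80 participants". The same section says that, in a pilot, power matters less than estimation, and that with promising results "these data will provide an estimate of the reliability of the intervention effect to inform power calculations for a larger RCT".

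**The concern.** Three features do not fit together.

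- **The design protects gender and the analysis ignores it.** If gender predicts initiation, an analysis that follows the randomisation uses the balance that blocking bought; the crude comparison does not.
- **The covariate rule selects on the wrong quantity.** Under valid randomisation, a baseline p-value measures chance imbalance, not how strongly a variable predicts outcome. The rule does also require a variable to be known as highly predictive, but the significance gate will usually keep such a variable out. For gender, blocking itself makes the gate nearly impossible to pass.
- **The power statement and the named test may not belong together.** Fisher's test is conservative at these event counts, and the text gives no alpha, sidedness or method.

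At stake is the quality of the effect estimate that is meant to feed the larger trial, and whether the statement of adequate power can be relied on.

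**Working it through.** **Inputs.** From the plan: control 10%, intervention 35% (10% + 25 points; 35/10 = 3.5, agreeing with the stated relative risk), 45 per arm, complete sample 80 (40 per arm), 1:1 allocation, Fisher's exact test, 95% CI. Assumed: alpha 0.05, for the test and for the baseline screen; all gender-specific rates, because the documents give none.

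**1. Reproduce the stated power.** Two-sided normal approximation with pooled null variance, n = 45, mean rate (0.10 + 0.35)/2 = 0.225:
- SE under the null = √(2 × 0.225 × 0.775 / 45) = 0.0880
- SE under the alternative = √((0.10 × 0.90 + 0.35 × 0.65)/45) = 0.0840
- z = (0.25 − 1.96 × 0.0880)/0.0840 = 0.922, so power = 82.2%

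This agrees with the plan's claim. At 40 per arm the same formula gives 77.4%.

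**2. Power of the named test.** Sum the binomial probabilities of every pair of event counts for which Fisher's p ≤ 0.05:

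| Fisher's exact test | 45/arm | 40/arm |
|---|---|---|
| Two-sided 0.05 | 76.1% | 71.7% |
| One-sided 0.05 | 85.2% | 81.5% |

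Two-sided, 48 per arm gives 79.8% and 49 gives 80.9%, so 80% needs 49 per arm. With 10% initiating in both arms, two-sided Fisher rejects about 2% of the time (2.0% at 45 per arm, 1.7% at 40).

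**3. How often the covariate screen fires.** For one predictor, 5%. For k independent predictors, 1 − 0.95^k: 10% for two and 14% for three. At 45 per arm a continuous predictor must differ by t(0.975, 88 df) × √(2/45) = 0.42 SD. With blocks formed within gender, the arms differ by at most a few men, so the chi-square test for gender effectively never reaches significance.

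**4. What stratifying by gender is worth.** Exact enumeration over both strata, comparing the uncorrected gender-stratified Cochran-Mantel-Haenszel (CMH) test with the uncorrected unstratified chi-square. This isolates stratification from Fisher's conservatism. Control vs intervention rates under three assumptions:
- A: no gender effect
- B: men 5 vs 25%, women 15 vs 45%
- C: men 2 vs 15%, women 18 vs 55%

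| Men/women, control; intervention | A: CMH vs crude | B | C | Gain (points) |
|---|---|---|---|---|
| 20/20; 20/20 (40/arm) | 79.4 vs 79.4% | 80.6 vs 79.7% | 84.4 vs 80.9% | 0 / +1 / +4 |
| 22/23; 22/23 (45/arm) | 83.5 vs 84.6% | 85.2 vs 85.2% | 88.3 vs 86.6% | −1 / 0 / +2 |
| 22/23; 23/22 (45/arm) | 83.5 vs 84.6% | 84.9 vs 84.1% | 88.2 vs 84.5% | −1 / +1 / +4 |
| 23/22; 22/23 (45/arm) | 83.5 vs 84.6% | 84.7 vs 86.0% | 88.3 vs 87.9% | −1 / −1 / +0.4 |

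At 45 per arm the answer depends on which arm holds the odd man. The Mantel-Haenszel estimate has a median SE of log relative risk 0 to 5% smaller than the crude one (for example 0.502 vs 0.526 in C at 40 per arm).

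**5. Effect measure.** At 10% vs 35% the relative risk is 3.5, but the odds ratio is (0.35/0.65)/(0.10/0.90) = 4.85. A logistic result reported without its measure could be misread.

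**The case against.** **Little is lost by omitting gender.** This stands. Without a gender effect, stratifying does not help, and the +4 requires the most extreme rates assumed. A reader might take +4 points as the general gain at 45 per arm; it is not, since it depends on the extra man being in the intervention arm.

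**The power figure is not shown to be an arithmetic error.** This stands too. It reproduces by a standard approximation, and the hypothesis is worded directionally, so a one-sided 0.05 Fisher test would satisfy the claim at both sizes. The 95% interval and the wording of the repeated test as one of association favour a two-sided reading but do not settle it. What remains is that alpha, sidedness and method are unstated, and the likeliest reading does not give 80%.

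**Fisher is a reasonable choice with so few events.** About 4 or 5 control initiations are expected (0.10 × 45 = 4.5). An uncorrected CMH test is asymptotic: its null rejection reaches 5.3% at 40 per arm in the cases checked, and a continuity correction gives most of the gain back (76 to 81% at 45 per arm). Replacing Fisher is therefore a trade-off, not a correction.

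**A pilot need not be held to power.** The plan says so itself. But it also declares the study adequately powered and intends the estimate for planning the next trial, so both should be stated accurately.

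Two further inferences are unsupported. The covariate rule does not threaten the false-positive rate: it looks at baseline data rather than outcomes, and the hypothesis is tied to Fisher in both places. Nor should the gender provision be read as a mere enrolment quota that permits large imbalances; the text describes blocked randomisation based on gender.

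**Conclusion.** The point holds as a modest one. The primary analysis omits the blocking factor, and the rule for admitting covariates will rarely admit a real predictor and effectively never gender. Validity is intact; the cost is up to about 4 power points and up to 5% in standard error under assumed gender effects, and nothing if gender does not matter. The stronger part of the case is pre-specification: no covariate, screening level or form is fixed, and the logistic model's role and effect measure are left open.

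Separately, the power claim fits a two-sided normal approximation, not a two-sided 0.05 Fisher test, which falls about 4 points short of 80% at 45 per arm and about 8 short at 40. That conclusion depends on the two-sided 0.05 reading.

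**What to change.** 1. Report a gender-stratified Mantel-Haenszel relative risk with 95% CI as the effect estimate, and say explicitly that blocks are formed within gender, if so.
2. For the test, either keep Fisher or name a gender-stratified test in advance. These are equal options: Fisher guarantees its size but is conservative; uncorrected CMH has more power but is asymptotic.
3. Present baseline data descriptively and drop the significance tests as the trigger for adjustment.
4. Pre-specify gender, plus any predictor the investigators can justify from prior data and its form, in a logistic model labelled supportive, with its effect measure stated.
5. State alpha and sidedness, and restate power for the test used. If Fisher stays: about 76% at 45 per arm and 72% at 40 two-sided, or 85% and 81% if one-sided 0.05 is intended.

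The cost is analysis-plan wording only. Gender is already recorded for randomisation, and no new data or participants are needed.

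### The stated power above 80% is not what the planned Fisher's exact test delivers: at two-sided 5% it is about 76% with 45 per arm and 72% with 40 per arm

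*Combined protocol and SAP*

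**What the plan says.** The primary data analysis paragraph of the combined protocol and SAP, just before Power/Sample Size Considerations, states the hypothesis directionally ("The hypothesis that The Treatment Ambassador Program will yield higher rates of ART initiation") and names the test: "by the completion of the intervention will be tested using Fisher's exact test". The estimated effect, it adds, "will be summarized in terms of a relative risk and 95% confidence interval". The Coding text under Process evaluation analysis repeats the relative risk and Fisher's test at 3 months, there described as "testing for an association between arm and initiation rate". It mentions no interval.

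Power/Sample Size Considerations, taking a maximum of 45 in each arm, says: "the probability is greater than 80 percent that the study will detect a difference of 25% in the percent who initiate ART". The assumed control rate is about 10%, so the intervention rate is 35% (relative risk 3.5). With attrition of up to 10%, the plan expects 80 complete participants from 90. The same section says that, for a pilot, power matters less than precise estimation.

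The documents do not give the significance level, the sidedness, the method behind the power figure, the method for the relative-risk interval, a rule for an arm with no starters, or a rule for which result governs if test and interval disagree.

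**The concern.** A power figure should describe the test that will be run. Fisher's test conditions on both margins and is conservative at this sample size, so its power falls below that of a normal-approximation formula. If the figure came from such a formula, the plan promises more than its own primary test can give.

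A second, smaller matter follows from the unnamed interval. Common relative-risk intervals are not obtained by inverting Fisher's test. The report could therefore show a non-significant p-value beside an interval that excludes 1, with nothing to say which is the result.

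At stake is how the pilot is read. A non-significant result would be interpreted against a stated power above 80%, and the relative risk and its interval are meant to feed the power calculation for a larger trial.

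**Working it through.** **Inputs.** From Power/Sample Size Considerations: control 10%, intervention 35%, up to 45 per arm, 80 complete participants (40 per arm). Assumed, because not stated: two-sided 5%, and independent participants.

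**Step 1: the plan's figure.** Pooled normal approximation:

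power = Φ[(Δ − 1.96·SE₀)/SE₁], with SE₀ = √(2·p̄(1−p̄)/n) and SE₁ = √((p₁(1−p₁)+p₂(1−p₂))/n).

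Here Δ = 0.25 and p̄ = (0.10+0.35)/2 = 0.225.

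- n = 45: SE₀ = √(2×0.225×0.775/45) = 0.0880; SE₁ = √((0.0900+0.2275)/45) = 0.0840; (0.25 − 0.1725)/0.0840 = 0.922; power 82.2%. This reproduces the claim.
- n = 40: SE₀ = 0.0934; SE₁ = 0.0891; (0.25 − 0.1830)/0.0891 = 0.752; power 77.4%.

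**Step 2: the planned test.** Exact power is the sum, over all tables with c control and t intervention starters, of Bin(c; n, 0.10) × Bin(t; n, 0.35), counting only tables the test rejects. The maximum type I error uses the same sum with a common rate in both arms, maximized over that rate.

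| Test | Power, 45/arm | Power, 40/arm | Maximum error, 45/arm |
|---|---|---|---|
| Fisher, two-sided 5% | 76.1% | 71.7% | 3.2% |
| Boschloo, two-sided 5% | 82.7% | 76.6% | 4.9% |
| Fisher, one-sided 5% (not stated in the plan) | 85.2% | 81.5% | – |

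Two-sided Fisher gives 79.8% at 48 per arm and 80.9% at 49, so it first passes 80% at 49. The plan's ceiling is 45.

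**Step 3: the interval, if it were log-Wald.** Limits are exp[ln RR ± 1.96·√(1/t + 1/c − 2/n)].

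- Example, 4/45 versus 12/45: RR = 3.0; SE = √(1/12 + 1/4 − 2/45) = 0.5375; lower limit exp(1.0986 − 1.0535) = 1.05. Fisher p = 0.051.
- Over all tables with starters in both arms, under 10% versus 35%: the interval excludes 1 with Fisher p > 0.05 in 4.6% of trials at 45 per arm and 2.4% at 40. The reverse does not occur.
- With no control starters the interval is undefined: 0.9⁴⁵ = 0.9% of trials at 45 per arm, 0.9⁴⁰ = 1.5% at 40.
- At 45 per arm, other interval methods give disagreement of 3.0% (log-Wald with 0.5 added) or 8.5% (score interval).

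**The case against.** **Sidedness.** The hypothesis is worded directionally, and a one-sided 5% Fisher test does exceed 80% at both sample sizes. This stands as a possibility. However, the plan states no one-sided level, it reports a 95% interval, and it elsewhere describes the comparison as a test of association. Two-sided 5% is the more natural reading, and the plan should say so.

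**Pilot context.** The plan puts estimation ahead of testing, focuses this phase on acceptability and feasibility, and ties no go/no-go rule to p < 0.05. This limits the consequences. It does not make the power figure correct, and it gives more reason to name the interval method.

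**Fisher is legitimate.** It is valid, justified by the randomization itself, and named consistently. Boschloo's error control assumes independent binomial outcomes, and with three Treatment Ambassadors outcomes may cluster. This stands: keeping Fisher is acceptable once its power is stated correctly.

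**Forty per arm.** The primary analysis includes everyone randomized, and initiation is sought in records as well as by self-report. If outcomes are available for all 90, the 45-per-arm figure applies. Even that is below 80%.

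**A stronger reading of the interval.** A reader might infer that the plan pairs Fisher with a mismatched interval and that the two contradict each other in about 5% of trials. The documents do not support that. They name no interval method, so no mismatch is shown. The rate depends on method, arm size and true effect, and for log-Wald with no effect (10% in both arms, 45 per arm) it is below 0.5%. Adding 0.9% to the 4.6% would count tables with no starters in an arm, where log-Wald gives no interval at all. That is a missing rule, not a contradiction.

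**Conclusion.** The power statement needs correcting. For 10% versus 35%, the named test at two-sided 5% has 76.1% power at 45 per arm and 71.7% at 40, not more than 80%. The shortfall against the normal approximation at 45 per arm is 82.2 − 76.1 = 6.1 points. This rests on two-sided 5%, independent outcomes and the plan's own rates. A declared one-sided 5% test would remove the discrepancy, but the plan declares none.

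A reader might also infer that Fisher is the wrong test or wastes power. That goes too far. Boschloo gains 6.6 points at 45 per arm (82.7 − 76.1) and 4.9 at 40 (76.6 − 71.7), but it does not reach 80% at 40, and choosing between two valid tests is a judgement. The unnamed interval method is a secondary gap in specification, not a demonstrated error.

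**What to change.** 1. State two-sided 5% for the primary test.
2. Choose one of these, before outcome data are seen by arm:
   - Keep Fisher's exact test and restate power as about 76% at 45 per arm and 72% at 40.
   - Use Boschloo's unconditional exact test and state power as about 83% and 77%, with maximum error 4.9%.
3. Name the relative-risk interval method. Either obtain the interval by inverting the same statistic as the chosen test, which also covers an arm with no starters, or state that the test governs when the two differ and say what is reported for such an arm. If Fisher is kept, the governing rule is the simpler route, because inverting the conditional test gives an interval for the odds ratio, not the relative risk.

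**Cost.** A few sentences of SAP text, with no new data or participants. Boschloo's test is less familiar to readers, and giving up Fisher's conservatism leaves less cushion if outcomes cluster by Treatment Ambassador. Keeping Fisher means accepting a stated power below 80%.
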